If a patient presents with a Grade 2 infusion reaction:

- The infusion should be stopped immediately.
- The patient should receive appropriate further treatment with an antihistamine and/or acetaminophen (paracetamol) or methylprednisolone (or equivalent) if clinically indicated.
- Once the symptoms have been resolved or reduced to \leq Grade 1 according to Investigator assessment, the infusion can be continued at an infusion rate of 50%. If, after one hour, the patient's symptoms do not return and vital signs are stable, the infusion rate may be increased every 30 minutes, as tolerated, to the baseline rate.

If a patient who developed a Grade 1 or 2 IRR receives further infusions, then pre-medication should be given before all subsequent infusions of MOR00208.

Management of Grade 3 IRRs

If a patient presents with a grade 3 IRR:

- The infusion should be stopped immediately.
- The patient must receive appropriate treatment with an antihistamine and/or acetaminophen (paracetamol) or methylprednisolone (or equivalent) and, if necessary, further medications (i.e., epinephrine, bronchodilator).
- Once the symptoms have been resolved or reduced to \leq Grade 1, and after having received appropriate prophylactic medication(s) as described above, the infusion may be resumed at an infusion rate of 25%. If, after 1 hour, the patient's symptoms do not return and vital signs are stable, the infusion rate may be increased to a maximum of 50%.
- If, after the resumption of infusion, symptoms return (irrespective of grade), the infusion must be stopped immediately and the infusion tubing should be disconnected from the patient. Based on the Investigator's decision the patient may receive further study drug(s), provided clinically appropriate precautions are undertaken. Infusion of MOR00208 should be discontinued permanently upon the third Grade 3 infusion reaction.

Management of Grade 4 IRRs

If a patient presents with a Grade 4 IRR:

- The infusion should be stopped immediately and the infusion tubing should be disconnected from the patient.
- The patient should receive appropriate treatment with an antihistamine and/or acetaminophen (paracetamol) or methylprednisolone (or equivalent) and, if necessary, further medications (i.e., epinephrine, bronchodilator).

The patient must not receive further infusions of MOR00208 that is judged by the Investigator to be the cause of the IRR, but should continue treatment with the other study drug as per protocol.

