8.6 Dose Modifications of MOR00208

In a phase I study of MOR00208 in CLL, the MTD was not reached and the drug was generally well tolerated, IRRs of grade 1 or 2 being the most common toxicities. Treatment-related grade 3 or 4 AEs occurred in 5 out of 27 patients and included neutropenia, thrombocytopenia, increased AST, febrile neutropenia, and TLS. There was one CLL patient with dose-limiting toxicity (DLT) of grade 4 neutropenia lasting ≥ 7 days with febrile neutropenia

Dose reductions of MOR00208 are not allowed during the course of the study due to the relatively mild AE profiles of MOR00208.

In the case of clinically significant grade ≥ 3 toxicities that are not described in Table 8 & Table 9 and Sections 8.9 & 8.10:

- MOR00208 doses should be omitted until the toxicity grading diminishes in severity to grade ≤ 1 or returns to a baseline grade, provided the condition was pre-existing at baseline
- Missed doses of MOR00208 should not be made up for. If the patient misses a subsequent MOR00208 dose, the second missed dose should be administered immediately after the toxicity resolves.
- During monthly treatment with MOR00208, every missed dose should be administered immediately after the toxicity resolves.

If the Investigator considers a clinical finding and/or laboratory parameter change to represent natural fluctuation or progression of the underlying disease, then it will be at the Investigator's discretion (and depend on the assessment of the individual risk/benefit ratio) to determine whether the patient should be dosed. The decision and rationale behind the decision should be documented in the source data.

For MOR00208 dose modification instructions for specific toxicities, see Table 8 & Table 9 and Sections 8.9 & 8.10.

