8.12 Treatment Accountability and Compliance

The pharmacist or other designated individual will maintain records of study treatment delivered to the study site; the inventory at the site; the distribution to and use by each patient; and the return of materials to the sponsor or disposal. These records should include dates, quantities, batch/serial numbers, expiration dates, in-clinic temperature log, and unique code numbers assigned to the product and study patients.

Patients will receive MOR00208 under the direct supervision of study personnel. Each administration volume or dose will be checked and the vial/outer package code and volume or dose per administration will be recorded in each patient's eCRF as well as in the source data.

At each visit after initiation of treatment, site staff will record compliance of patients with their assigned regimen. Patients will be instructed to bring unused/partially used/empty medication containers of idelalisib or venetoclax back for inspection on Day 1 of each cycle, starting with Cycle 2, or on the EOT visit as compliance will be assessed by tablet counts.

Patients are to be reminded of the importance of compliance with their assigned regimen, with an emphasis on taking their study drug on schedule, and maintaining the prescribed interval between doses.

Investigators will maintain records that document adequately that the patients were provided with the correct study treatment kits and will reconcile the products received from the drug dispensing center. Drug accountability will be checked by the field monitor during site visits and at the completion of the trial.

Noncompliance in general is defined as taking $\leq 80\%$ or $>120\%$ of one MOR00208 dose and/or $\leq 80\%$ or $>120\%$ of the idelalisib or venetoclax intake per cycle during any outpatient evaluation period.

Moreover, one MOR00208 dose can be missed between Cycles 1 and 3, between Cycles 4 and

12 and one dose between Cycles 13 and 24 without the patient being non-compliant. Note that MOR00208 dose omissions due to toxicity are covered in Sections 8.6 and 8.9.

Discontinuation for noncompliance is at the Investigator's discretion and is to be noted on the eCRF.

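### The general MOR00208 toxicity rules (Section 8.6 default and Table 9) do not exempt infusion-related reactions, so as worded they let dosing resume where Section 8.4 forbids it

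*Protocol*

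**What the plan says.** **Section 8.4** is the protocol's dedicated rule for MOR00208 IRRs.
- After a Grade 3 reaction, once symptoms have settled, "the infusion may be resumed at an infusion rate of 25" percent. The permanent stop comes later: "Infusion of MOR00208 should be discontinued permanently upon the third Grade 3 infusion reaction".
- After a Grade 4 reaction: "The patient must not receive further infusions of MOR00208 that is judged by the Investigator to be the cause of the IRR".

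**Section 8.6** sets the general rule for MOR00208 after toxicity.
- Its default covers clinically significant Grade 3 or higher "toxicities that are not described in Table 8 & Table 9 and Sections 8.9 & 8.10".
- The action is that "MOR00208 doses should be omitted until the toxicity grading diminishes in severity to grade" 1 or lower, or back to a pre-existing baseline grade.
- A first missed dose is not made up. A second missed dose, and every dose missed in the monthly phase, is to be given at once when the toxicity has resolved.
- The section ends: "For MOR00208 dose modification instructions for specific toxicities, see Table 8 & Table 9 and Sections 8.9 & 8.10".

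**Table 8 and Section 8.9** (Cohort A) have no entry for infusion reactions.

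**Table 9 in Section 8.10** (Cohort B) has a row for all Grade 3 or 4 non-hematologic toxicities. At the first occurrence MOR00208 may restart after recovery to Grade 1 or baseline. At later occurrences it may restart at the physician's discretion. The row neither exempts IRRs nor mentions Section 8.4.

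**The concern.** A site deciding on the next infusion after a severe reaction would naturally turn to the section on MOR00208 dose modifications, or to its cohort's toxicity table. Neither leads to Section 8.4. Read as written, each allows or directs MOR00208 again in a patient whom Section 8.4 bars. What is at stake is renewed exposure after a life-threatening reaction, in a study whose primary purpose is the safety of two combinations not previously given in the clinic.

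**Working it through.** The protocol gives no figure to reproduce here, so the check sets the rules side by side.

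1. *Does an IRR fall inside the general rules?* Table 3 grades IRRs on the CTCAE scale. An IRR is not a blood-count abnormality or tumor lysis syndrome, so in Table 9 it belongs to the non-hematologic row. Table 9 sits in the section on the venetoclax combination and is read here as governing Cohort B only. For Cohort A, neither Table 8 nor Section 8.9 describes an IRR, so the 8.6 default applies. The exception is an IRR that is also a serious allergic reaction, which Section 8.9.6 covers and which therefore leaves the default.

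2. *What does each rule tell the site to do with MOR00208?*

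| Event | Section 8.4 | General rule |
|---|---|---|
| Grade 4 IRR judged caused by MOR00208, Cohort B | No further MOR00208 | Table 9: may restart after recovery |
| Third Grade 3 IRR, Cohort B | Permanent stop | Table 9: may restart at the physician's discretion |
| Grade 4 IRR judged caused by MOR00208, Cohort A | No further MOR00208 | 8.6: withhold until Grade 1 or lower, or baseline |
| Third Grade 3 IRR, Cohort A | Permanent stop | 8.6: same as the row above |

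3. *Does 8.6 only imply resumption?* No. Its instructions on a second missed dose and on missed monthly doses positively direct administration once the toxicity resolves.

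4. *Does waiting for recovery protect the patient?* Hardly. The note to Table 3 says infusion reactions generally clear within 24 hours after the infusion ends. The shortest gap between scheduled infusions is Day 1 to Day 4 of Cycle 1, which is 4 − 1 = 3 days. The recovery condition would therefore usually be met before the next dose is due.

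5. *How often could this arise?* The phase I results in Table 2 list no Grade 3 or 4 infusion reaction among 27 patients, 16 of them at 12 mg/kg. Grade 1 or 2 reactions occurred in 18 of 27 (66.7%). No rate is given for a Grade 4 IRR or for a third Grade 3 IRR.

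**The case against.** The strongest reply is that Section 8.4 is written for exactly this event, is graded, and uses prohibitive language for Grade 4. Table 9 only permits, and it is introduced as recommendations drawn from the FDA Prescribing Information. A site that declines a permission breaches nothing, so in Cohort B both texts can be obeyed by following Section 8.4. Severe IRRs are also events of special interest, reportable within 24 hours. The entry criteria exclude patients with a previous severe allergic reaction to antibody therapy.

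Much of this stands, and it is why the point is minor. It does not remove the point. The 8.6 text on missed doses is an instruction, not a permission. Reporting follows the event and does not tell the site which rule governs the next infusion.

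A reader might infer more than the documents support:
- *That Section 8.12 is part of the conflict.* It says that "MOR00208 dose omissions due to toxicity are covered in Sections 8.6 and 8.9", but only to qualify how many missed doses count as non-compliance. It also leaves out 8.10, so it is not a complete list.
- *That the rules conflict on venetoclax.* Table 9 interrupts it, while Section 8.4 bars MOR00208 "but should continue treatment with the other study drug as per protocol". The closing words bring in the rest of the protocol, and Section 8.8.1 points to Table 9 for venetoclax-related toxicities. A reaction to MOR00208 can be read as outside it.
- *That Sections 8.4 and 8.9.6 are irreconcilable in Cohort A.* They overlap only when a severe IRR is also a serious allergic reaction. There the mandatory stop of both drugs in 8.9.6 outranks the permission to resume after Grade 3 in 8.4. Stopping idelalisib under 8.9.6 is itself in line with the protocol. A precedence sentence would help but is optional.

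**Conclusion.** The point holds as a minor patient-safety correction: two general rules omit an exception for IRRs, and one of them directs dosing that Section 8.4 prohibits. It rests on reading Table 9 as a Cohort B table, on treating an IRR as a non-hematologic toxicity and, for the Grade 4 ban, on the investigator judging MOR00208 to be the cause.

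Few patients are likely to be affected, but the number cannot be estimated. A reader might turn the phase I zero count into an upper limit and an expected number per cohort. That would bound any Grade 3 or 4 IRR, a broader event than a Grade 4 or third Grade 3 reaction followed by a site overlooking Section 8.4.

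Nor can one infer that the primary endpoint is untouched. A re-exposed patient may react again, which would enter the adverse event counts and possibly the grades. The exposure, infusion-count, compliance and action-taken summaries depend on the same decision. The documents give no basis for sizing any of these effects.

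**What to change.** - In the 8.6 default, and in the Table 9 row for Grade 3 or 4 non-hematologic toxicities, add: *except MOR00208 infusion-related reactions, see Section 8.4*.
- Add Section 8.4 to the pointer sentence that closes 8.6.
- Optionally, state in Section 8.4 that in Cohort A Section 8.9.6 takes precedence when the reaction is anaphylaxis or a serious allergic reaction.

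The cost is a few words in 8.6 and Table 9, plus one sentence in 8.4 if the option is taken. No new data, visits or patients are needed.

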8.5 Definition for Tumor Lysis Syndrome and Prophylaxis in Cohort B

8.5.1 Definition of Tumor Lysis Syndrome

The tumor lysis syndrome occurs when tumor cells release their contents into the bloodstream, either spontaneously or in response to therapy, leading to the characteristic findings of hyperuricemia, hyperkalemia, hyperphosphatemia, and hypocalcemia. These electrolyte and metabolic disturbances can progress to clinical toxic effects, including renal insufficiency, cardiac arrhythmias, seizures, and death due to multiorgan failure (Howard et al., 2011). Clinical manifestations may include nausea, vomiting, lethargy, oedema, fluid overload, congestive heart failure, cardiac dysrhythmias, seizures, muscle cramps, tetany, syncope and possibly sudden death. The clinical manifestations may have their onset prior to initiation of cytotoxic therapy but more commonly present within 12–72 h after administration of cytotoxic therapy (Cairo et Bishop, 2004).

In the current classification system the tumor lysis syndrome can be classified as laboratory or clinical as described in Table 4. In laboratory tumor lysis syndrome, two or more metabolic abnormalities must be present during the same 24-hour period within 3 days before the start of therapy or up to 7 days afterward. Clinical tumor lysis syndrome requires the presence of laboratory tumor lysis syndrome plus an increased creatinine level, seizures, cardiac dysrhythmia, or death (Howard et al., 2011).

Table 4: Definitions of Laboratory and Clinical Tumor Lysis Syndrome

Metabolic Abnormality	Criteria for Classification of Laboratory Tumor Lysis Syndrome	Criteria for Classification of Clinical Tumor Lysis Syndrome
Hyperuricemia	Uric acid >8.0 mg/dL (475.8 µmol/L) in adults or above the upper limit of the normal range for age in children	
Hyperphosphatemia	Phosphorus >4.5 mg/dL (1.5 mmol/L) in adults or >6.5 mg/dL (2.1 mmol/L) in children	
Hyperkalemia	Potassium >6.0 mmol/L	Cardiac dysrhythmia or sudden death probably or definitely caused by hyperkalemia
Hypocalcemia	Corrected calcium <7.0 mg/dL (1.75 mmol/L) or ionized calcium <1.12 (0.3 mmol/L) *	Cardiac dysrhythmia, sudden death, seizure, neuromuscular irritability (tetany, paresthesias, muscle twitching, carpedal spasm, Trousseau's sign, Chvostek's sign, laryngospasm, or bronchospasm), hypotension, or heart failure probably or definitely caused by hypocalcemia

Acute kidney injury **	Not applicable	Increase in the serum creatinine level of 0.3 mg/dL (26.5 µmol/L) (or a single value >1.5 times the upper limit of the age-appropriate normal range if no baseline creatinine measurement is available) or the presence of oliguria, defined as an average urine output of <0.5 mL/kg/hr for 6 hr
------------------------	----------------	---

* The corrected calcium level in milligrams per deciliter = measured calcium level in milligrams per deciliter + 0.8 × (4 – albumin in grams per deciliter).

** Acute kidney injury is defined as an increase in the creatinine level of at least 0.3 mg per deciliter (26.5 µmol per liter) or a period of oliguria lasting 6 hours or more. By definition, if acute kidney injury is present, the patient has clinical tumor lysis syndrome (Levin et al., 2007)

8.5.2 Prophylaxis for Tumor Lysis Syndrome in Cohort B

Patients enrolling in Cohort B will be assessed for TLS risk and categorized in a risk category at screening. Prior to the initiation of the first doses of MOR00208 medical prophylaxis for TLS should be initiated according to the institutional standard of care.

Administration of venetoclax can cause rapid reduction in tumor and thus poses a risk for TLS in the initial 5-week ramp-up phase with venetoclax. Changes in blood chemistries consistent with TLS that require prompt management can occur as early as 6 to 8 hours following the first dose and at each dose increase. The risk of TLS is a continuum based on multiple factors, including tumor burden and comorbidities. Therefore, tumor burden assessments, including radiographic evaluation (e.g., CT scan), blood chemistry (potassium, uric acid, phosphorus, calcium, and creatinine) should be performed in all patients and the pre-existing abnormalities should be corrected prior to initiation of treatment with venetoclax. Reduced renal function (creatinine clearance [CrCl] <80 mL/min) further increases the risk. The risk may decrease as tumor burden decreases. [Table 5](#) describes the recommended TLS prophylaxis and monitoring during treatment with venetoclax based on tumor burden determination from clinical trial data. Importantly, all patients in Cohort B, who participate in the safety run-in phase, will be hospitalized on the day of the first two dose escalations of venetoclax (C1D8 and C1D15).

Table 5: Recommended TLS Prophylaxis Based on Tumor Burden From Clinical Trial Data of Venetoclax

Tumor Burden		Prophylaxis		Blood Chemistry Monitoring ^{c,d}
		Hydration ^a	Antihyperuricemics	Setting and Frequency of Assessments
Low	All LN <5 cm AND ALC <25 x10 ⁹ /L	Oral (1.5-2 L)	Allopurinol ^b	Outpatient 
 • Pre-dose, 6 to 8 hours, 24 hours at first dose of 20 mg and 50 mg • Pre-dose at subsequent ramp-up doses
Medium	Any LN 5 cm to <10 cm OR ALC ≥25 x10 ⁹ /L	Oral (1.5-2 L) and consider additional intravenous	Allopurinol	Outpatient 
 • Pre-dose, 6 to 8 hours, 24 hours at first dose of 20 mg and 50 mg • Pre-dose at subsequent ramp-up doses • Consider hospitalization for patients with CrCl <80mL/min at first dose of 20 mg and 50 mg; see below for monitoring in hospital
High	Any LN ≥10 cm OR ALC ≥25 x10 ⁹ /L AND any LN ≥5 cm	Oral (1.5-2 L) and intravenous (150-200 mL/hr as tolerated)	Allopurinol; consider rasburicase if baseline uric acid is elevated	In hospital at first dose of 20 mg and 50 mg 
 • Pre-dose, 4, 8, 12 and 24 hours Outpatient at subsequent ramp-up doses 
 • Pre-dose, 6 to 8 hours, 24 hours

Note: Consider all patient comorbidities before final determination of prophylaxis and monitoring schedule.

^aAdminister intravenous hydration for any patient who cannot tolerate oral hydration.

^bStart allopurinol or xanthine oxidase inhibitor 2 to 3 days prior to initiation of venetoclax.

^cEvaluate blood chemistries (potassium, uric acid, phosphorus, calcium, and creatinine); review in real time.

^dFor patients at risk of TLS, monitor blood chemistries at 6 to 8 hours and at 24 hours at each subsequent ramp-up dose

8.6 Dose Modifications of MOR00208

In a phase I study of MOR00208 in CLL, the MTD was not reached and the drug was generally well tolerated, IRRs of grade 1 or 2 being the most common toxicities. Treatment-related grade 3 or 4 AEs occurred in 5 out of 27 patients and included neutropenia, thrombocytopenia, increased AST, febrile neutropenia, and TLS. There was one CLL patient with dose-limiting toxicity (DLT) of grade 4 neutropenia lasting ≥ 7 days with febrile neutropenia

Dose reductions of MOR00208 are not allowed during the course of the study due to the relatively mild AE profiles of MOR00208.

In the case of clinically significant grade ≥ 3 toxicities that are not described in Table 8 & Table 9 and Sections 8.9 & 8.10:

- MOR00208 doses should be omitted until the toxicity grading diminishes in severity to grade ≤ 1 or returns to a baseline grade, provided the condition was pre-existing at baseline
- Missed doses of MOR00208 should not be made up for. If the patient misses a subsequent MOR00208 dose, the second missed dose should be administered immediately after the toxicity resolves.
- During monthly treatment with MOR00208, every missed dose should be administered immediately after the toxicity resolves.

If the Investigator considers a clinical finding and/or laboratory parameter change to represent natural fluctuation or progression of the underlying disease, then it will be at the Investigator's discretion (and depend on the assessment of the individual risk/benefit ratio) to determine whether the patient should be dosed. The decision and rationale behind the decision should be documented in the source data.

For MOR00208 dose modification instructions for specific toxicities, see Table 8 & Table 9 and Sections 8.9 & 8.10.

8.7 Dose Modifications of Idelalisib

In the event of severe or life-threatening toxicities related to idelalisib, the drug must be withheld until the toxicity is resolved. If resuming idelalisib after interruption, reduce the dose to 100 mg twice daily. Re-escalation to 150 mg twice daily is allowed at the Investigator's discretion.

Recurrence of severe or life-threatening idelalisib-related toxicity upon rechallenge should result in permanent discontinuation of idelalisib.

For dose modification instructions for specific toxicities related to idelalisib, see Section 8.9 and Table 8.

8.8 Dose Modifications of Venetoclax

8.8.1 General Rules

Dose should be interrupted or reduced for toxicities. For patients who have had a dosing interruption greater than 1 week during the first 5 weeks of ramp-up phase or greater than

2 weeks when at the daily dose of 400 mg, reassess for risk of TLS to determine if reinitiation with a reduced dose is necessary (e.g., all or some levels of the dose ramp-up schedule).

For dose modification instructions for specific (hematologic and other) toxicities related to venetoclax see [Table 6](#) below and [Table 9](#) in Section 8.10.

Table 6: Dose Modification for Toxicity During Venetoclax Treatment

Dose at Interruption, mg	Restart Dose, mg ^a
400	300
300	200
200	100
100 ^b	50
50 ^b	20
20 ^b	10

^aDuring the ramp-up phase, continue the reduced dose for 1 week before increasing the dose.

^bDose reductions below 100 mg are not allowed after the ramp-up phase.

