8.1.3 Venetoclax

[figure not shown]
Venetoclax 10 mg, 50 mg and 100 mg tablets as commercially available for oral administration. They are to be stored at or below 30°C (86°F; US only).

Venetoclax dose should be administered according to a weekly ramp-up schedule over 5 weeks to the recommended daily dose of 400 mg. Figure 2 illustrates this initial ramp-up. Dosing schedule for ramp-up phase as follows, daily dose of venetoclax: 20 mg 1st week of combination treatment, 50 mg 2nd week, 100 mg 3rd week, 200 mg 4th week and 400 mg 5th week and thereafter. The 5-week ramp-up dosing schedule, starting on C1D8, is designed to gradually reduce tumor burden (debulk) and decrease the risk of tumor lysis syndrome (TLS). Assessment of patient-specific factors for level of risk of TLS and prophylaxis for TLS should be performed prior to first dose of venetoclax (see Section 8.10.1).

The first 4 weeks of venetoclax treatment will be supplied with respective venetoclax tablets, according to the ramp-up schedule. Once the ramp-up phase is completed, the 400 mg dose is achieved using 100 mg tablets supplied as monthly package of 120 tablets.

Venetoclax should be taken as scheduled orally once daily until disease progression or unacceptable toxicity is observed. Venetoclax tablets should be taken with a meal and water at approximately the same time each day. Tablets should be swallowed whole and not chewed, crushed, or broken prior to swallowing. If the patient misses a dose within 8 hours of the time it is usually taken, the patient should take the missed dose as soon as possible and resume the normal daily dosing schedule. If a patient misses a dose by more than 8 hours, the patient should not take the missed dose and should resume the usual dosing schedule the next day. If the patient vomits following dosing, no additional dose should be taken that day. The next prescribed dose should be taken at the usual time.

Figure 2: Ramp-up Dosing Schedule for Venetoclax

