8.8.3 Dose Modifications After the Ramp-up Phase

Dose should be interrupted or reduced for toxicities according to [Table 6](#) and [Table 9](#).

Note: Dose modifications below 100 mg daily dose are not allowed, once the individual highest dose of venetoclax is reached. Patients who need dose reductions below 100 mg daily dose should discontinue venetoclax treatment permanently and may proceed with MOR00208 treatment only, per discussion between the Investigator and sponsor's medical monitor.

8.8.4 Dose Modifications of Venetoclax for Use with CYP3A, P-gp, BCRP and OATP Inhibitors

Concomitant use of venetoclax with strong or moderate CYP3A inhibitors (e.g., strong: ketoconazole, conivaptan, clarithromycin, indinavir, itraconazole, lopinavir, ritonavir, telaprevir, posaconazole and voriconazole; moderate: erythromycin, ciprofloxacin, diltiazem, fluconazole, verapamil) or inducers (e.g., strong: carbamazepine, phenytoin, rifampin, St. John's wort; moderate: bosentan, efavirenz, etravirine, modafinil, nafcillin) during ramp-up phase is

contraindicated. Co-administration of CYP3A4 inducers may lead to decreased venetoclax exposure and consequently a risk for lack of efficacy. Concomitant use of venetoclax with strong CYP3A inhibitors increases venetoclax exposure (i.e., C_{max} and AUC) and may increase the risk for TLS during ramp-up phase. For patients who have completed the ramp-up phase and are on a steady daily dose of venetoclax, reduce the venetoclax dose by at least 50% when moderate CYP3A inhibitors and 75% when *strong* CYP3A inhibitors must be used concomitantly, but not below 100 mg. Patients should be monitored more closely for signs of toxicities and the dose may need to be further adjusted. The venetoclax dose that was used prior to initiating the CYP3A inhibitor should be resumed 2 to 3 days after discontinuation of the inhibitor.

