Grade 3 or 4 neutropenia with infection or fever or Grade 4 hematologic toxicities (except lymphopenia)	1 st occurrence	Interrupt venetoclax. To reduce the infection risks associated with neutropenia, granulocyte-colony stimulating factor (G-CSF) may be administered with venetoclax if clinically indicated. Once the toxicity has resolved to Grade 1 or baseline level , venetoclax therapy may be resumed at the same dose.	Interrupt MOR00208. To reduce the infection risks associated with neutropenia, granulocyte-colony stimulating factor (G-CSF) may be administered with MOR00208 if clinically indicated. Once the toxicity has resolved to Grade 1 or baseline level , MOR00208 therapy may be resumed.

MorphoSys AG Proprietary Information

NCI CTCAE Grade ^a	Occurrence	Action	
		Venetoclax	MOR00208
	2 nd and subsequent occurrences	Interrupt venetoclax. Consider transfusion and growth factor support as clinically indicated in accordance with institutional guidelines. Follow dose reduction guidelines in Table 6 when resuming treatment with venetoclax after resolution. A larger dose reduction may occur at the discretion of the physician, but not below 100 mg daily dose after the ramp-up phase.	Interrupt MOR00208. Consider transfusion and growth factor support as clinically indicated in accordance with institutional guidelines. MOR00208 therapy may be resumed after resolution, as follows: Neutropenia: Withhold MOR00208 and monitor ANC at least weekly until ANC $\geq 0.5 \times 10^9/L$ and/or neutropenic fever or infection is resolved. Thereafter, may resume as per protocol. Thrombocytopenia: withhold MOR00208 until platelet count reach $\geq 25 \times 10^9/L$ and monitor at least weekly. Thereafter, may resume as per protocol. Anemia: Withhold MOR00208 until Grade 3 and monitor at least weekly. Thereafter, may resume as per protocol.

Consider discontinuing venetoclax for patients who require dose reductions to less than 100 mg for more than 2 weeks during the ramp-up phase. Dose modifications below 100 mg are not allowed after the ramp-up phase and patient should discontinue venetoclax treatment.

^aAdverse reactions were graded using NCI CTCAE version 4.03.

^bClinical TLS was defined as laboratory TLS with clinical consequences such as acute renal failure, cardiac arrhythmias, or sudden death and/or seizures.

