12.1 Determination of Sample Size

The primary endpoint of this study is the incidence and severity of AEs in Cohort A (MOR00208 combined with idelalisib) and Cohort B (MOR00208 combined with venetoclax) and will be analyzed descriptively. In each cohort 12 patients will be enrolled. No formal sample size calculation was performed and no formal statistical hypothesis testing is planned.

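### After a venetoclax interruption of more than 2 weeks at 400 mg, Protocol 8.8.1 permits a restart through 20 and 50 mg, while the 100 mg floor in 8.8.3 makes no exception for such a restart

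*Protocol*

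**What the plan says.** Protocol 8.8.1 sets two interruption triggers for venetoclax: a "dosing interruption greater than 1 week during the first 5 weeks of ramp-up phase", or one longer than "2 weeks when at the daily dose of 400 mg, reassess for risk of TLS". After either, the site is to "determine if reinitiation with a reduced dose is necessary (e.g., all or some levels of the dose ramp-up schedule"). Section 8.1.3 gives the schedule as 20, 50, 100, 200 and 400 mg daily, one level per week from Cycle 1 Day 8.

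The floor appears in three main places:

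- **8.8.3, note:** "Dose modifications below 100 mg daily dose are not allowed, once the individual highest dose of venetoclax is reached". Patients who would need less should stop venetoclax permanently and may go on with MOR00208 alone, after discussion with the sponsor's medical monitor.
- **Table 6, footnote b (within 8.8.1):** reductions below 100 mg are barred once ramp-up is over.
- **Table 9, closing note (8.10):** "Dose modifications below 100 mg are not allowed after the ramp-up phase and patient should discontinue venetoclax treatment".

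Section 8.10.2 repeats the floor for larger reductions made for hematologic toxicity.

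**The concern.** A patient who has reached 400 mg and then misses more than 2 weeks falls under both rules. Section 8.8.1 opens the whole ramp-up schedule, including its two lowest levels. Section 8.8.3 closes those two levels to anyone who has reached their highest dose, and sends a patient who needs them off the drug.

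Two things are at stake. The first is consistent handling of a restart whose purpose is to limit TLS risk. The second is the meaning of the safety tables. SAP 4.7.2 counts any venetoclax dose reduction, transient or permanent, and SAP 4.10.1.7.1 tabulates adverse events leading to discontinuation by drug. A re-ramped patient could appear in the first summary and a patient taken off venetoclax in the second. Which one applies would depend partly on the section the site followed.

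**Working it through.** There is no planned figure to reproduce, so the check compares the texts and adds a short day count.

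**1. Do the two rules reach the same patient?** The second trigger in 8.8.1 is defined at 400 mg, the top of the schedule. A patient there has reached the highest dose, which is the condition in the 8.8.3 note. So they do.

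**2. Which levels conflict?** Levels in 8.1.3: 20, 50, 100, 200, 400 mg. Below 100 mg: 20 and 50 mg, that is 2 of 5. At one week per level, a full re-ramp would spend 2 × 7 = 14 days under the floor.

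**3. Is a restart a dose modification in the protocol's own usage?** Section 8.8.1 stands under the heading on venetoclax dose modifications and describes the restart as being at a reduced dose. Section 8.8.2 also uses the term for changes that follow a dosing interruption. The 8.8.3 note is not limited to modifications made for toxicity.

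**4. Is there an exemption?** Sections 8.1.3, 8.5.2, 8.8.1 to 8.8.4, 8.10, 8.10.1, 8.10.2, 8.11, 9.2.8 and 9.3.2.6 contain none for a TLS-risk restart after the highest dose.

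**5. Is the situation foreseen?** Section 8.11 expects treatment to continue after a drug-related interruption of up to 28 days. Interruptions of 15 to 28 days at 400 mg are therefore within what the protocol plans to restart.

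**6. When does the floor begin?** The 8.8.3 note uses the highest dose reached. Tables 6 and 9 use the end of ramp-up. On schedule:

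| Marker | Calculation | Study day |
|---|---|---|
| First 400 mg dose (8.8.3) | 8 + 4 × 7 | 36 |
| First day after a 5-week ramp-up (Tables 6 and 9) | 8 + 5 × 7 | 43 |

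The two markers are a week apart if ramp-up lasts the five weeks stated in 8.1.3.

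**7. Weight of one patient.** 1/12 = 8.3 percentage points of a cohort rate, for the approximately 12 patients planned per cohort.

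**The case against.** The best defense is that the rules have different subjects. Tables 6 and 9 are titled as toxicity tables, and 8.8.3 opens with toxicity. The 8.8.1 sentence deals with TLS risk after a gap in dosing. A patient repeating the schedule might also be regarded as back in ramp-up, where doses below 100 mg are allowed. SAP 4.7.2 lists permanent reductions only to 300, 200 or 100 mg, which would suit a floor on sustained doses. Moreover, 8.8.1 offers the ramp-up levels only as an example, and a site that restarted at 100 mg or above would satisfy both sections. Section 8.8.3 also brings in the medical monitor, which limits divergence between sites.

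Much of this stands for Tables 6 and 9: either reading could reconcile them with 8.8.1. Neither reading is written down, however, and neither fits the 8.8.3 note. That note speaks of dose modifications without restriction, and it turns on a dose having been reached, which starting again does not undo. It is also true that 8.8.1 permits 20 and 50 mg without prescribing them. A permission in one section and a prohibition in another still conflict.

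A reader might infer more than the documents support:

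- **Contradictory triggers in week 5.** The two triggers are joined by an or, so meeting either calls for reassessment. Sections 9.2.8 and 9.3.2.6 also require it when an interruption moves a ramp-up dose to an unscheduled visit, and before each escalation.
- **A ramp-up that ends after four weeks.** This rests mainly on the supply statement in 8.1.3, "The first 4 weeks of venetoclax treatment will be supplied with respective venetoclax tablets, according to the ramp-up schedule", which describes packaging and does not define the phase.
- **Permanent discontinuation under Table 9.** Its note says the patient should discontinue. Among the floor passages, only 8.8.3 says permanently.

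**Conclusion.** The conflict holds between 8.8.1 and the 8.8.3 note. For a patient interrupted more than 2 weeks at 400 mg, 2 of the 5 levels that 8.8.1 allows are barred by 8.8.3, and no passage settles which prevails. Table 6 footnote b and the Table 9 note state the same floor with a different starting marker, so they need to be brought into line too. The conclusion assumes that a restart below the previous dose counts as a dose modification, as 8.8.1 and 8.8.2 suggest.

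The number of patients affected cannot be derived. It is tempting to start from the 41% rate of Grade 3 or 4 neutropenia quoted in 8.10.2. Table 9, however, interrupts only for neutropenia with infection or fever, or for Grade 4 hematologic toxicity. The same section gives febrile neutropenia in 5% and venetoclax dose adjustments in 9.6%. None of these figures gives the share interrupted for more than 2 weeks at 400 mg.

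No test or power statement is touched, since Protocol 12.1 says: "No formal sample size calculation was performed and no formal statistical hypothesis testing is planned". The consequence lies in consistent conduct and in how descriptive reduction and discontinuation counts are read. Nothing here judges which dosing rule is right.

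**What to change.** Reconcile 8.8.1 with the 8.8.3 note, Table 6 footnote b and the Table 9 note (and 8.10.2, which repeats the floor). State whether the 100 mg floor applies to a restart made for TLS risk after the highest dose has been reached. Use one marker for when the floor begins in all of these places. The choice of rule and of marker is the sponsor's.

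The cost is a few sentences in a protocol amendment or clarification letter. No new assessments are needed.
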